After randomization, the 40 participants in the NRT condition (matched for age, sex, IQ, and smoking severity) will receive specialized preparation for NRT administration. In approximately week 5, these participants will begin a standard 8 to 10 week NRT treatment regimen according to recommended label usage (For individuals who smoke more than 10 cigarettes per day: 21mg daily weeks 1-6, 14mg daily weeks 7-8, 7mg daily weeks 9-10. For individuals who smoke 10 or less cigarettes per day: 14mg daily for weeks 1-6, 7mg daily for weeks 7-8; FDA label, PDR.net). Participants in the NRT condition will have brief weekly counseling meetings and provide exhaled CO samples to test for smoking status in weeks 6, 7, 9, 11, and 13. These individuals will also have follow-up meetings at approximately 3, 6, and 12 months post target-quit date to assess smoking status. Participants randomized to the NRT condition who are also completing the MRI portion of the study (n=25) will complete their second MRI scan in week 5, immediately before initiating use of the nicotine patch. For both treatment conditions, MRI participating volunteers who provide biologically verified (i.e., breath CO), and self-report seven-day point prevalence abstinence at 3 months post-TQD will receive a final follow-up MRI scan.

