The first (optional) MRI scan may occur as part of a voluntary NIDA approved sub-study protocol, which is a large-scale (N=2500) investigation of genetic polymorphisms associated with substance dependence. If participants agree to participate in this sub-study, the related MRI scan will be completed after study-screening, and will produce an MRI scan of clinical quality to be examined for incidental findings by a Johns Hopkins Hospital (JHH) neuroradiologist. Participants who decline to complete the NIDA sub-study will receive a clinical MRI scan at their first MRI scanning visit to be examined for incidental findings by a JHH neuroradiologist. The next (required) MRI scan will take place in approximately week 2 of treatment after an initial orientation meeting, and before randomization in week 3. The following (required) MRI scan will scan will occur in approximately week 5 of treatment. For the psilocybin condition this scan will

occur one day after psilocybin administration. For the NRT condition this scan will occur immediately before initiating NRT administration. A final, conditional MRI scan will take place at 3-month follow-up only for participants demonstrating biologically verified seven-day point-prevalence smoking abstinence at that time. After completing the 6-month follow-up all participants initially randomized to the NRT condition will be eligible to undergo additional (optional) meetings including a high-dose psilocybin session. However, no further MRI scanning will be conducted after the 3-month time point.

Participants will be asked to abstain from smoking for 24 hours before all MRI scanning sessions, as verified by measures of exhaled breath CO. MRI scans will last roughly 4 to 6 hours, and be conducted at the NIDA IRP building adjacent to the BPRU by a trained MRI operator. A trained study staff member will be present during all MRI scanning sessions. Any incidental findings will be communicated by the JHH neuroradiologist to the NIDA IRP Medical Advisory Investigator, who will transmit incidental findings to [name], the Hopkins study team physician. [name] will report any incidental findings to participants at an in-person meeting, over the phone, or via mail as deemed appropriate commensurate with the significance of the findings.

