Assessment of Smoking Cessation: Participants will complete smoking assessments (including biological verification and other measures as shown in section 7) at 1 to 2 week intervals throughout the course of the study. These assessments will include biological verification of smoking status with breath carbon monoxide during the 13-week treatment period. Additionally, urine cotinine samples will be collected at screening, and at 3, 6, and 12-month follow-ups. Participants will have meetings in weeks 6, 7, 9, 11, and 13 after their initial TQD to provide self-report data on smoking behavior, exhaled breath samples, and to complete questionnaires. All participants will have follow-up meetings at 3, 6, and 12 months post-TQD, or at 3 and 6 months post-TQD, and 6 months post-psilocybin administration for participants in the NRT condition who choose to undergo an optional psilocybin session. Breath samples may be taken remotely using an individually assigned mobile CO breath monitor device, and urine samples may be provided remotely by mail or tested at home.

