#### Longitudinal measures (Smoking related):

#### Carbon monoxide breath and cotinine urine samples as biological measures of smoking:

These two measures are widely used in smoking cessation studies and provide advantages that complement each other. The carbon monoxide measure, assessed using expired air samples (e.g., Bedfont Smokerlyzer, Bedfont iCO mobile smokerlyzer) can detect very recent smoking and provides immediate results to study staff, but cannot detect smoking that occurred over 24 hours ago. The cotinine assay is collected with urine samples and will not provide results for several days because samples must be sent to an outside laboratory (e.g., Friends Research Institute). However, cotinine assays provide a larger time window of detection, with the ability to detect smoking that has occurred during approximately the last 6 days (SRNT Subcommittee on Biological Verification, 2002). Breath samples may be taken remotely using an individually assigned mobile CO breath monitor, and urine samples may be provided remotely by mail or tested at home.

*Fagerström Test for Nicotine Dependence* (FTND): This 6-item questionnaire is widely used to characterize the level of dependence of cigarette smokers (Heatherton, Kozlowski, Frecker, & Fagerström, 1991).

*Smoking History Questionnaire* (SHQ): This questionnaire permits collecting smoking data such as age of smoking initiation, parent and peer smoking behavior, history of quit attempts, and current level of smoking (DiClemente et al., 1991).

*Smoking Abstinence Self-Efficacy* (SASE): This questionnaire provides a measure of a smoker's confidence in his or her ability to not smoke in 20 challenging hypothetical situations (DiClemente et al., 1985).

*The Wisconsin Smoking Withdrawal Scale* (WSWS): The WSWS is a 28-item questionnaire designed to assess withdrawal DSM-IV symptoms and other signs of withdrawal (Welsch et al., 1999), and provides 7 construct subscales (anger, anxiety, sadness, concentration, craving, sleep, and hunger). The WSWS subscales have shown good reliability and have been validated in smoking abstinence and nicotine replacement therapy studies (Shiffman et al., 2004).

*Questionnaire on Smoking Urges* (QSU): This 32-item questionnaire of smoking craving provides two dimensions (anticipation of pleasure from smoking, and anticipation of relief from negative affect and withdrawal), and has shown sensitivity to smoking cessation (Tiffany & Drobes, 1991).

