#### Functional Neuroimaging (fMRI; for MRI participating volunteers only):

Smoking cessation and withdrawal have been well documented to affect brain function, including resting state functional connectivity, and smoking related cue-reactivity (McLernon et al., 2007; Sutherland et al., 2012). In order to examine the underlying neurobiological mechanisms associated with psilocybin-facilitated smoking cessation, and identify potential brain based mediating factors predictive of treatment outcomes, up to 60 participants will undergo two to three brain scans collecting fMRI data while performing the tasks detailed below. The first scanning session will take place in week 2 of treatment, after a 24-hour period of smoking abstinence. The second will occur in approximately week 5 of treatment (i.e., one day after the psilocybin session, or immediately before initiating NRT), after another 24-hour period of smoking abstinence. Participants who provide biologically verified (i.e., breath CO), and selfreport seven-day point prevalence abstinence at 3 months post-TQD will receive a final followup MRI scan at that time. Functional neuroimaging will be conducted at NIDA IRP by trained MRI operators under the supervision of [name]. In addition to these scanning sessions, MRI participating volunteers will also be given the option to participate in a preliminary MRI scan through a NIDA-approved sub-study protocol. Either the primary study scans or the preliminary study scan will include a clinical scan to be examined for incidental findings.

State of the art, multimodal imaging will be performed on a Siemens 3T Trio scanner, located at the NIDA-IRP (intramural research program). Participants' heads will be placed inside the RF coil and held in place by a head restraint that generally consists of soft foam padding. For most scanning experiments, a blipped, gradient-echo, echo-planar image (EPI) pulse sequence (e.g. TE = 27ms) is used with a TR of about 2 seconds. Specific imaging parameters (e.g. number of slices, slice angle, TR, TE, flip angle etc.) may be changed in order to maximize signal integrity. A "watchdog" program runs continuously on the MRI computer during all pulse sequences and ensures that no scanning parameter ever exceeds FDA guidelines.

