#### 9. Payment and Remuneration

### a. Detail compensation for participants including possible total compensation, proposed bonus, and any proposed reductions or penalties for not completing the protocol.

Volunteers will not receive monetary compensation for the treatment portion of the study (i.e, treatment meetings, follow-ups). However, MRI participating volunteers (n=60) will receive an hourly compensation of \$20/hr. for all MRI scanning days, including participation in the preliminary NIDA sub-study protocol (possible total compensation=\$480). Funding for this compensation will be provided by NIDA IRP. In order to match potential earnings between all MRI participating volunteers, those who do not undergo a paid 3-month follow-up MRI scan (i.e., who are smoking at that time) will be compensated at a \$20/hr. rate for their time during the 3-month follow-up. Funding for this compensation will be provided by the research study budget. No penalties will be assessed for not completing the protocol. Volunteers will receive free parking vouchers for all scheduled study visits.

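### Seven-day abstinence for the 3-month MRI scan is biologically checked only by breath CO, which covers no more than the 24 hours already required before any scan; the imaging analysis should use the cotinine collected at 3 months

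*Combined protocol and SAP*

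**What the plan says.** Section 3.a (Study design) offers the final scan to MRI volunteers in either arm with "biologically verified (i.e., breath CO), and self-report seven-day point prevalence abstinence at 3 months post-TQD". Section 6.b (Functional Neuroimaging) repeats the rule: "Participants who provide biologically verified (i.e., breath CO), and selfreport seven-day point prevalence abstinence". The part of section 3.a on MRI scanning sessions speaks of biological verification without naming the assay.

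Section 6.b, on the biological measures of smoking, says that CO "cannot detect smoking that occurred over 24 hours ago". It describes cotinine as a complement, "with the ability to detect smoking that has occurred during approximately the last 6 days", with results after several days because an outside laboratory is used. Section 3.a also states the general scan condition, to be verified by CO: "Participants will be asked to abstain from smoking for 24 hours before all MRI scanning sessions". The part of section 3.a on assessing smoking cessation says that "urine cotinine samples will be collected at screening, and at 3, 6, and 12-month follow-ups".

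For 7-day abstinence at 6 months, section 3.f requires cotinine, CO and self-report together. Section 6.c plans to analyse resting-state MRI by relapse status and by treatment success or failure. It does not define relapse status or connect it to the 3-month cotinine.

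On pay, section 9.a gives $20 per hour for scanning days. It gives the same rate for follow-up time to MRI volunteers who have no 3-month scan because they are smoking. The stated purpose begins "In order to match potential earnings between all MRI" volunteers.

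**The concern.** The scan rule claims biological verification of a seven-day state, but the assay it names covers about one day. That day is the one on which everyone attending a scan has to abstain anyway. A participant who smoked earlier in the week, stopped for the scan and reported seven clean days would meet every condition.

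The 3-month scan is the last one in the study and the only one that can address persisting effects on connectivity, which are part of the secondary objective. It is limited to abstainers among at most 30 participants per arm, so the numbers will be small. A few misclassified smokers would blur any contrast tied to abstinence. The study is open-label, and the more informative sample is due at the same 3-month time point.

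**Working it through.** **1. Cover of the seven-day window.** Count day 1 as the 24 hours before the scan. The detection windows are those in section 6.b.

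| Requirement | Day 1 | Days 2-6 | Day 7 |
|---|---|---|---|
| 24 h abstinence before any scan | yes | no | no |
| CO check | yes | no | no |
| Cotinine, if used | yes | yes | no |
| Self-report | yes | yes | yes |

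CO covers 1/7 = 14% of the days and cotinine 6/7 = 86%. These are shares of days, not detection probabilities. The first two rows are identical, so CO adds nothing to the scan condition.

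**2. Would the patch confuse cotinine?** The patch course starts around the target quit date and lasts 8 to 10 weeks (56 to 70 days). Taking 3 months as 84 to 91 days, it ends between 84 - 70 = 14 and 91 - 56 = 35 days before the visit. Both exceed the 6-day window, so a patch used on schedule should not make the 3-month sample positive. Late patch use or other nicotine products could.

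**3. Size of misclassification (illustration only).** Let p be the true share abstinent for seven days, and m the share of smokers who both abstain for 24 hours and misreport. The documents give neither. The share of smokers in the scanned group is

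(1 - p)m / [p + (1 - p)m].

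For the share left after cotinine, assume 90% sensitivity and no loss of true abstainers, and replace m by 0.1m.

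| Assumed p | Assumed m | CO + self-report | With cotinine |
|---|---|---|---|
| 60% | 5% | 0.02/0.62 = 3.2% | 0.002/0.602 = 0.3% |
| 40% | 10% | 0.06/0.46 = 13.0% | 0.006/0.406 = 1.5% |
| 20% | 20% | 0.16/0.36 = 44.4% | 0.016/0.216 = 7.4% |
| any | 0% | 0% | 0% |

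The width of this range shows that the size is unknown.

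**4. Pay.** The stated maximum of $480 reproduces as 4 sessions x 6 h x $20. At 3 months:

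- The scan lasts 4-6 h, which pays $80-120.
- The follow-up of an unscanned MRI volunteer lasts 2-4 h, which pays $40-80.
- The gap runs from $80 - $80 = $0 to $120 - $40 = $80.

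Section 3.b says that visits without MRI, potentially including the 3-month one, are about 4-5 h shorter, which suggests that the scan is added to the follow-up meeting. If a scanned participant's follow-up hours are paid as well, the gap is the whole scan fee, $80-120. The documents do not settle which applies.

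**The case against.** **The quoted rule schedules a scan; it does not define an analysis group.** This is correct. Section 6.c uses relapse status and treatment success or failure, and section 3.f ties treatment failure at 6 months to cotinine. The plan therefore does not say that imaging participants will be classified by CO alone. What remains is that relapse status is undefined, and that the only 3-month imaging criterion in the text relies on CO and self-report.

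**Cotinine is already collected and cannot book a scan.** Both parts are true. A result that takes days cannot decide a scan at that visit, so CO is reasonable for booking. The delay does not prevent classification afterwards, and no section says that the sample will be used that way.

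**A smoker must also give a false report.** This is true and it limits the problem. CO is also measured in weeks 6, 7, 9, 11 and 13, and Timeline Follow-Back at all treatment meetings. These make continuous undetected smoking harder, but they do not verify the seven days before the 3-month scan.

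**The primary endpoint's nicotine-product rule is itself self-report.** This is also true. Under section 6.c a positive cotinine counts as abstinent if the participant reports non-smoking nicotine, so someone willing to misreport could still pass. Hence the sensitivity analysis in the fix.

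**A reader might infer that abstainers are paid more and so have a reason to misreport.** The documents do not support this. The hourly rate is the same, extra money pays for extra hours, and nothing in the text shows that the difference affects reporting.

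**Conclusion.** The concern holds in a limited form. For the 3-month scan, the one biological test named cannot verify seven-day abstinence and adds nothing to the general 24-hour scan condition. The plan leaves unused, for imaging, a sample that it collects at the same time point and that its own 6-month standard requires. This follows from the protocol's stated detection windows and needs no outside figure.

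A reader might go further and conclude that the scanned group does contain current smokers, or that the imaging contrasts are diluted by a known amount. Neither follows. The documents give no misreporting rate and no expected abstinence rate, and with no misreporting there is no contamination.

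The effect is confined to exploratory imaging in a pilot study. The 6-month primary outcome uses both CO and cotinine and is untouched. The change is still worth making before the imaging data are analysed, because it is cheap.

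The pay point is secondary. The rule equalises the hourly rate but does not guarantee equal earnings. The gap is $0-80 on the stated visit lengths and possibly more if the scan is added to a paid follow-up visit.

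**What to change.** 1. Keep CO plus self-report for booking the 3-month scan.
2. In section 6.c, define 3-month abstinence and relapse status for the imaging analysis by the urine cotinine already collected at 3 months, together with CO and self-report. This is the section 3.f standard applied at 3 months.
3. Apply the section 6.c Timeline Follow-Back rule for non-smoking nicotine. Add a sensitivity analysis that codes every cotinine-positive participant as non-abstinent.
4. Report scans that fail cotinine separately, with their number by arm.
5. In section 9.a, either set the 3-month payment so that earnings match, or reword the aim to equal hourly pay.

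Items 2 to 4 need a few sentences of analysis text and no new assay. The downside is that a few scans may leave an already small abstinent group. The sensitivity analysis may also remove some true abstainers who use other nicotine products. Rewording the pay aim costs nothing. The cost of matching the amounts depends on visit lengths that the documents give only as ranges.

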#### All standard study meetings, meeting content, and duration are summarized here:

\* Indicates MRI procedures to be completed only by participants who are eligible for MRI scanning (n=60).

a Times listed in the table are approximate.

bMRI Scan 4 only for participants showing biologically verified abstinence at 3-month follow-up.

Intentions and expectations for the psilocybin session will be discussed. Furthermore, a structured cognitive-behavioral smoking cessation intervention will be implemented throughout the course of these meetings to prepare participants for smoking abstinence and potential withdrawal. Throughout the preparatory meetings, participants will be encouraged to view the psilocybin session as providing an opportunity for deep reflection about the role of smoking in their lives. The purpose of the psilocybin session is to enhance motivation for initiating a quit attempt. Procedures for drug administration and the conduct of the session will be similar to

procedures used in our previous (Griffiths et al., 2006, 2008, 2011) and ongoing studies with psilocybin (IRB # NA\_00001390 in cancer patients; IRB # NA\_00020767 in healthy adults), and are described below in the section "Conduct of Psilocybin Sessions."

Participants will meet with study staff for debriefing one or two days after the psilocybin session. Participants will then meet weekly with study staff for 2 weeks after their psilocybin session (i.e., in weeks 6 and 7), and at 2-week intervals until the end of the 13-week study treatment (i.e., in weeks 9, 11, and 13). The general purpose of the meetings following the session is to provide a context for discussing and integrating experiences from the psilocybin session, and to provide support for smoking cessation. Additional contact hours will be scheduled if it is judged that the participant would benefit from further meetings with study staff to discuss experiences from the session or provide additional support for smoking abstinence. Aside from the psilocybin session and MRI scan visits (if applicable), all meetings may be held remotely using a secure online platform, including use of remote CO monitoring and mailed in or at home urine sample testing.

Meetings Before and After TQD (NRT Condition): Before the target-quit date participants in the NRT condition will meet with one or more of the study staff on at least 3 occasions, for a minimum of 4 hours of contact time before drug administration. Some flexibility in scheduling will be allowed to account for unexpected absences such as travel commitments or illnesses. The main purpose of the participant-staff meetings is to prepare participants for NRT transdermal patch administration, and to deliver a cognitive-behavioral smoking cessation intervention identical to that received by participants in the psilocybin condition. During these meetings study staff will answer any questions related to NRT, examine motivations to quit smoking, and encourage preparation for smoking cessation on the target-quit date. Participants in this condition will be provided with NRT patches and instructed how to use the patches, which may be mailed to participants to reduce unnecessary in-person visits. In week 5, participants in the NRT condition will begin a standard 8 to 10 week course of NRT for smoking cessation. For MRI participating volunteers, nicotine patches will be initiated directly after their week 5 MRI scan. All participants in the NRT condition will have five additional counseling meetings with study staff in weeks 6, 7, 9, 11, and 13, where they will provide self-report and breath samples to assess smoking status and complete study questionnaires. The study physician will be available during the study to discuss any potential side effects or medical issues. Participants will complete questionnaires and provide breath and urine samples to evaluate smoking status at approximately 3, 6, and 12 months post-TQD.

**Optional Meetings / Psilocybin Session (NRT Condition):** After completing the 6-month follow-up, participants initially randomized to the NRT condition will be eligible to undergo an optional high-dose (30mg/70kg) psilocybin session. If they choose to take part, they will receive two weekly preparation meetings, one high-dose psilocybin session and next-day integration meeting, and two weekly follow-up meetings. For individuals unsuccessful in their smoking cessation attempt using NRT, this session will serve as an additional quit attempt and provide further smoking cessation efficacy data on psilocybin pharmacotherapy in treatment-resistant populations. For participants who successfully quit smoking using NRT, this session will focus on promoting long-term abstinence. For participants from the NRT condition who choose to take part in the optional psilocybin session, their remaining follow-up meeting will be shifted to take place at 6 months after their optional psilocybin session (in place of their original 12-month follow-up). Participants who choose not to take part in this process will not be penalized, and will be asked to complete the study as originally planned through 12-month follow-up.

